5.3 Exclusion Criteria

Subjects who meet any of the following criteria will be excluded from the study.

1. Hypersensitivity to MYK-461 or any of the components of the MYK-461 formulation.
2. Presence of any medical condition that precludes exercise stress testing.
3. History of sustained ventricular tachyarrhythmia.
4. History of syncope with exercise within past 6 months.
5. Active infection.
6. Persistent atrial fibrillation or atrial fibrillation at Screening or history of paroxysmal atrial fibrillation with resting rate documented >100 bpm within 1 year of screening.
7. Has QTc Fridericia (QTcF) > 500 ms, or any other ECG abnormality considered by the investigator to pose a risk to subject safety (e.g., second degree atrioventricular block type II).
8. Aortic stenosis or fixed subaortic obstruction.
9. History of LV systolic dysfunction (LVEF < 45%) at any time during their clinical course.

10. History of obstructive coronary artery disease (stenosis of >70% of luminal diameter in one or more coronary arteries).
11. History of malignancy of any type, with the following exceptions: in situ cervical cancer more than 5 years prior to Screening or surgically excised non-melanomatous skin cancers more than 2 years prior to Screening.
12. Positive serologic test at Screening for infection with human immunodeficiency virus (HIV), hepatitis C virus (HCV), or hepatitis B virus (HBV).
13. Positive test for alcohol or drugs of abuse at Screening.
14. History or evidence of any other clinically significant disorder, condition, or disease (with the exception of those outlined above) that, in the opinion of the investigator or MyoKardia physician, would pose a risk to subject safety or interfere with the study evaluation, procedures, or completion.
15. Participated in a clinical trial where the subject received any investigational drug (or is currently using an investigational device) within 30 days prior to Screening, or at least 5 times the respective elimination half-life (whichever is longer).
16. Current use of tobacco- or nicotine-containing products exceeding 10 cigarettes per day or equivalent.
17. Part A: Subjects who in the opinion of the investigator require ongoing therapy with β -blockers, calcium channel blockers, or disopyramide. Subjects on any of these medications who, in the opinion of the investigator, can safely be withdrawn are eligible as long as medication is discontinued at least 14 days prior to the Screening visit.
18. Part B: Subjects who in the opinion of the investigator require ongoing therapy with calcium channel blockers or disopyramide. Subjects on any of these medications who, in the opinion of the investigator, can safely be withdrawn are eligible as long as medication is discontinued at least 14 days prior to the Screening visit. Prior treatment with cardiotoxic agents such as doxorubicin or similar, or current treatment with antiarrhythmic drugs that have negative inotropic activity, e.g., flecainide or propafenone.
19. Unable to comply with the study restrictions/requirements, including the number of required visits to the clinical site.
20. Is employed by, or is a relative of someone employed by MyoKardia, the investigator, or his/her staff or family.

5.4 Screening and Enrollment

An informed consent form (ICF) must be signed and dated by the subject before the subject is asked to discontinue HCM background therapy and before any study-specific tests or procedures may be performed.

Each subject will be assigned an identification number when informed consent has been obtained. This number will be used to identify the subject throughout the study and should appear on all study-related documentation.

Subjects that fail to meet all inclusion criteria or present with an exclusion criterion may be re-screened. Refer to Study Reference Manual for re-screening criteria.

5.5 Withdrawal and Replacement of Subjects

5.5.1 *Withdrawal from the Study*

Study participants may withdraw from further participation in the study at any time and for any reason. The degree to which a study participant withdraws can vary, and efforts will be made to collect important safety data if feasible and the study participant agrees. Study participants can:

- Withdraw from treatment and agree to participate in the Early Termination and End of Study (EOS) visits
- Withdraw from treatment and agree to participate in the Early Termination visit
- Withdraw from treatment and all follow-up

The investigator or MyoKardia may withdraw a study participant from treatment in the study for any of the following (or other) reasons:

- AE
- Noncompliance with study procedures/restrictions
- Study termination by MyoKardia

In all cases, the reason(s) for study withdrawal will be recorded in the source document and on the appropriate electronic case report form (eCRF).

5.5.2 *Replacement of Subjects*

Subjects who do not receive MYK-461 may be replaced. Subjects who drop out of the study for reasons other than AEs after receiving study medication may be replaced at the discretion of MyoKardia.

All data from subjects who receive at least 1 dose of IMP will be documented and maintained in the clinical trial database.

6 RANDOMIZATION AND BLINDING PROCEDURES

6.1 Randomization

Subjects will not be randomized to treatment in this study.

6.2 Blinding

Treatment will not be blinded in this study.

7 STUDY TREATMENT

All subjects will receive MYK-461 in an open-label manner.

IMP is defined as MYK-461. Study medication is used throughout this protocol to refer to IMP as well as any other protocol-required medications (note that for this protocol there are no other required study medications).

7.1 MYK-461, Administration, and Schedule

Study medication will consist of MYK-461 immediate release oral tablets, supplied in 4 strengths: 2 mg, 5 mg, 10 mg, and 20 mg. MYK-461 tablets are uncoated and plain and white in appearance. The 2 mg and 5 mg tablets are round-convex in shape and of different sizes, while the 10 mg and 20 mg tablets are oval shaped of different sizes.

MYK-461 tablets are manufactured according to current Good Manufacturing Practice (cGMP) regulations. They will be supplied in high-density polyethylene bottles with induction seals and child resistant caps at 30 count per bottle. All study medication will be labeled according to applicable local regulatory guidelines.

The MYK-461 tablets must be stored at controlled room temperature at 20°C to 25°C (68°F to 77°F) in the packaging supplied by MyoKardia. Study medication at the investigational site will be stored in a secure area with access limited to authorized study personnel.

IMP will be supplied to subjects at least every 4 weeks in 30-count high-density polyethylene bottles that are appropriately labeled, with written instructions for daily dosing. The subjects will be instructed to store the MYK-461 tablets/bottles in a cool dry place. Drug should be taken with approximately 8 ounces of water.

7.2 Treatment Compliance

All subjects will return their IMP dosing containers, including unused study medication, to the site for tablet counts. Refer to the Pharmacy Manual for details.

Subjects should be instructed to take the study medication at approximately the same time every day (\pm 4 hours). If the dosing window is missed, the subject should not take study medication that day. Subjects should never receive 2 doses of MYK-461 within a 12-hour period.

On study visit days, subjects should wait until they reach the clinic to take their study medication.

7.3 Dose Adjustment

All subjects in Part A will be assigned to a starting dose of oral MYK-461 based on body weight for doses ≥ 10 mg, which they will receive QD for 4 weeks. Subjects in Part B will be assigned a starting dose of 2 mg. At the Week 4 visit, dose adjustment may be performed based on the predetermined criteria in [Section 4, Table 1 \(Part A\) and Table 2 \(Part B\)](#). The subject will subsequently receive that dose from Week 5 (Day 29) through Week 12.

7.4 Hepatotoxicity Stopping and Rechallenge Rules

Subjects with abnormal hepatic laboratory values (e.g., alkaline phosphatase [ALP], aspartate aminotransferase [AST], alanine aminotransferase [ALT], total bilirubin [TBL], or international normalized ratio) or signs/symptoms of hepatitis may meet the criteria for withholding of study medication or other protocol-required therapies. Withholding is either permanent or conditional depending on the clinical circumstances discussed below (as specified in the US Food and Drug Administration (FDA) Guidance for Industry–Drug Induced Liver Injury: Premarketing Clinical Evaluation, July 2009).

7.4.1 *Criteria for Permanent Withholding of MYK-461 Due to Potential Hepatotoxicity*

MYK-461 should be discontinued permanently and the subject should be followed according to the recommendations in [Appendix 3](#) for possible drug-induced liver injury (DILI), if all of the criteria below are met:

- $TBL > 2 \times$ upper limit of normal (ULN) or international normalized ratio > 1.5
- AND increased AST or ALT, if the baseline value was $< ULN$ and AST or ALT elevation is $> 3 \times ULN$
- AND no other cause for the combination of laboratory abnormalities is immediately apparent; important potential causes for abnormal AST/ALT or TBL values include, but are not limited to the following:
 - obstructive gall bladder or bile duct disease
 - viral or alcoholic hepatitis (e.g., hepatitis A/B/C/D/E, Epstein-Barr virus, cytomegalovirus, herpes simplex virus, varicella)
 - hypoxic or ischemic hepatopathy or congestive hepatopathy in association with significant right sided heart failure
 - concomitant administration of other hepatotoxins, including drugs that inhibit bilirubin glucuronidation (e.g., indinavir, atazanavir, irinotecan) or herbal or dietary supplements
 - heritable disorders causing impaired glucuronidation (e.g., Gilbert syndrome); α -1 antitrypsin deficiency
 - autoimmune hepatitis
 - nonalcoholic steatohepatitis (NASH) or other “fatty liver disease”

If an alternative cause for hepatotoxicity is identified or less stringent conditions developed than what is noted above, determine whether study medication and other protocol-required therapies should be permanently or temporarily discontinued based on subject population and/or severity of the hepatotoxicity or event, as deemed appropriate for the safety of the subject.

7.4.2 *Criteria for Conditional Withholding of MYK-461 Due to Potential Hepatotoxicity*

For subjects who do not meet the criteria for permanent withholding of study medication outlined above, MYK-461 should be withheld if ANY of the following criteria are met, and the subject should be evaluated for DILI:

- Elevation of either AST or ALT, regardless of baseline AST or ALT value, if:
 - $> 8 \times \text{ULN}$ at any time
 - $> 5 \times \text{ULN}$ and $< 8 \times \text{ULN}$ for ≥ 2 weeks
 - $> 5 \times \text{ULN}$ and $< 8 \times \text{ULN}$ and unable to adhere to enhanced monitoring schedule
- OR: clinical signs or symptoms that are, in the opinion of the investigator, consistent with hepatitis (such as right upper quadrant pain/tenderness, fever, nausea, vomiting, jaundice, rash or eosinophilia $> 5\%$). If such signs or symptoms are coupled with ALT or AST elevations $> 3 \times \text{ULN}$, study medication should be withheld.
- OR: TBL $> 3 \times \text{ULN}$ at any time
- OR: ALP $> 8 \times \text{ULN}$ at any time

MYK-461 should be withheld pending investigation into alternative causes of DILI. If study medication is withheld, the subject should be followed according to recommendations in [Appendix 3](#) for possible DILI. Rechallenge may be considered if an alternative cause, such as acute hepatitis B infection, is discovered and the laboratory abnormalities resolve to normal or baseline ([Section 7.4.3](#)).

7.4.3 *Criteria for Rechallenge of MYK-461 After Potential Hepatotoxicity*

The decision to rechallenge the subject should be discussed and unanimously agreed by the investigator, IDMC, and Sponsor.

If signs or symptoms recur with rechallenge, then MYK-461 should be permanently discontinued. Subjects who clearly meet the criteria for permanent discontinuation (as described in [Section 7.4.1](#)) should never be rechallenged.

7.5 *Guidelines for the Management of an Exaggerated Pharmacologic Effect*

Beta-adrenergic agonists are known to counteract the pharmacologic activity of MYK-461 in nonclinical studies. If a subject experiences AEs potentially related to reduced cardiac output,

administration of therapeutic doses of a β -adrenergic agonist (e.g., 5 to 10 $\mu\text{g}/\text{kg}/\text{min}$ dobutamine infusion) should be considered. Additional supportive measures, e.g., intravenous volume supplementation and/or the use of arterial vasoconstrictor agents (α -adrenergic agonists) may complement the use of a β -adrenergic agonist. Aside from this specific advice regarding the role of a β -adrenergic agonist, appropriate care will be determined by the treating medical personnel.

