5.2 Inclusion Criteria

Each subject must meet the following criteria to be enrolled in this study.

1. Able to understand and comply with the study procedures, understand the risks involved in the study, and provide written informed consent according to federal, local, and institutional guidelines before the first study-specific procedure.
2. Men or women 18 to 70 years of age at the Screening visit.
3. Diagnosed with HCM (hypertrophied and non-dilated left ventricle in absence of systemic or other known cause), with LV wall thickness ≥ 15 mm at time of initial diagnosis or ≥ 13 mm with a positive family history of HCM.
4. Body mass index (BMI) 18 to 37 kg/m², inclusive, at the Screening visit, calculated using the institution's standard formula.
5. All safety laboratory parameters (chemistry, hematology, and urinalysis) within normal limits (laboratory reference range) at the Screening visit as assessed by the central laboratory, or if outside of the limits must meet both of the following criteria:
 - considered by the investigator to be clinically unimportant
 - if a liver function test result, must be $< 1.5 \times$ the upper limit of the laboratory reference range.
6. Has documented LVEF $\geq 55\%$ at the Screening visit as determined by the investigator and the investigational site's echocardiography laboratory.
7. Resting LVOT gradient ≥ 30 mmHg and post-exercise peak LVOT gradient ≥ 50 mm Hg at the Screening visit as determined by the investigator and the investigational site's echocardiography laboratory.
8. NYHA functional class II or higher, judged by the investigator to be due to LVOT obstruction.
9. Has adequate acoustic windows, in the judgment of the investigator and the investigational site's echocardiography laboratory, to enable accurate TTEs.
10. Female subjects must not be pregnant or lactating and, if sexually active, must be using one of the following acceptable birth control methods from the Screening visit through 3 months after the last dose of investigational medicinal product (IMP). Hormonal contraceptives are not considered highly effective contraception for this study because MYK-461 could reduce the effectiveness of hormonal contraceptives.
 - Double-barrier method (e.g., vasectomy or male using a condom and female using a diaphragm or cervical cap)

- Barrier (e.g. male using a condom) plus non-hormonal intrauterine device (IUD) or intrauterine system (IUS)

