10 EVALUATION, RECORDING, AND REPORTING OF ADVERSE EVENTS

10.1 Definitions

10.1.1 Adverse Event

An AE is any untoward medical occurrence, or the deterioration of a preexisting medical condition (other than the condition that is being treated by the study) associated with the use of a study medication in humans, whether or not it is considered related to the study medication. An AE (also referred to as an adverse experience) can therefore be any unfavorable and unintended sign (e.g., tachycardia, enlarged liver, clinically important abnormal laboratory result or diagnostic procedure), subject-reported symptom (e.g., nausea, chest pain), or evidence of any disease activity temporally associated with the use of a study medication, whether or not related to the study medication.

In clinical studies, an AE can include an undesirable medical condition occurring at any time after the subject has signed informed consent, including run-in or washout periods, even if no specific treatment has been administered.

Preexisting medical conditions (other than natural progression of the disease being studied) judged by the investigator or subject to have worsened in severity or frequency or changed in character during the protocol-specified AE reporting period will be reported as AEs or SAEs as appropriate.

Imaging-based assessments of decrease in contractility are not considered AEs unless associated with symptoms or signs of clinical concern on the part of the investigator. Such events should be categorized as an AE defined in terms of those symptoms or signs.

An AE or SAE can also be a complication that occurs as a result of protocol-mandated procedures (e.g., invasive procedures such as biopsies).

For MyoKardia to collect additional information about clinically important laboratory results or diagnostic tests (e.g., blood, ECG, imaging), at a minimum, the following abnormalities should be captured on the AE eCRF:

- Any test result that meets the definition of an SAE
- Any clinically important test abnormality that suggests a disease and/or organ toxicity that has worsened or is new (e.g., $>3\times$ deviation from the upper or lower limit of the analyzing laboratory reference range, or as otherwise specified in the protocol)
- Any test abnormality that required the subject to have study medication discontinued or interrupted or in the clinical judgment of the investigator.

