- Any test abnormality that required the subject to receive specific corrective therapy, close observation, more frequent follow-up assessment, or further diagnostic investigation.

The term AE is used generally to include any AE whether serious or non-serious.

10.1.2 *Serious Adverse Event*

An SAE is an AE that fulfils one or more of the following criteria in the opinion of the investigator or MyoKardia:

- Results in death
- Is immediately life-threatening (places the subject at immediate risk of death from the event as it occurred)
- Requires in-subject hospitalization or prolongation of existing hospitalization
- Results in persistent or significant disability or incapacity or substantial disruption of the ability to conduct normal life functions
- Results in a congenital abnormality or birth defect
- Is an important medical event that may not result in death, be life-threatening, or require hospitalization, but may be considered an SAE when, based upon appropriate medical judgment, it may require medical or surgical intervention to prevent one of the outcomes listed above.

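### Subjects admitted with both AST and ALT at or above ULN fall outside the mandatory liver stop in Protocol 7.4.1 and the matching SAP count

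*Protocol*

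**What the plan says.** **Entry.** Inclusion criterion 5 (Protocol 5.2) accepts an out-of-range safety laboratory value if the investigator considers it clinically unimportant and, "if a liver function test result, must be" below 1.5 × ULN.

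**Permanent stop.** Protocol 7.4.1 requires three things together: TBL > 2 × ULN or INR > 1.5; "AND increased AST or ALT, if the baseline value was" below ULN and the value now exceeds 3 × ULN; and no other immediately apparent cause. No threshold is given for a baseline at or above ULN. A closing paragraph leaves cases where "less stringent conditions developed than what is noted above" to a case-by-case decision.

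**Conditional hold.** Protocol 7.4.2 applies at any baseline, "Elevation of either AST or ALT, regardless of baseline AST or ALT value, if" it is > 8 × ULN at any time, or > 5 and < 8 × ULN either for at least 2 weeks or without adherence to enhanced monitoring. Separate triggers are signs or symptoms of hepatitis, TBL > 3 × ULN and ALP > 8 × ULN. INR is not a trigger.

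**Rechallenge.** Under 7.4.3, subjects who clearly meet 7.4.1 "should never be rechallenged". For others: "The decision to rechallenge the subject should be discussed and unanimously agreed by the investigator, IDMC, and Sponsor".

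**Reporting.** Appendix 3 requires an SAE report within 24 hours for cases meeting the Section 7.4 criteria. It restates these in parentheses as 3 × ULN for AST/ALT with 2 × ULN for TBL, and describes the trial's eligibility criteria as requiring normal liver function.

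**Analysis.** SAP 9.2 identifies DILI by the Section 7.4 criteria. It also summarises subjects with TBL > 2 × ULN, or with AST/ALT > 3 × ULN and a baseline below ULN.

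**The concern.** The stop rule appears to be written for a population with normal baseline transaminases, which is not the population that inclusion 5 admits. Because every limb of 7.4.1 must be met, a subject with both enzymes at or above ULN at baseline cannot meet it at any on-study value. Section 7.4.2 does cover such a subject, but only at much higher limits and without an INR limb.

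Three things are lost for this subject: the mandatory stop on a combined transaminase and bilirubin (or INR) signal, the absolute bar on rechallenge, and inclusion in the SAP's transaminase and combined DILI counts. Protocol 8.1 says little is known about the risks of repeat daily dosing, and post-baseline chemistry is scheduled only at Weeks 4, 8, 12 and 16. When a combined signal is found, the protocol should say what follows.

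**Working it through.** The plan gives no figure to reproduce. The check applies the rules literally to example subjects.

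**Inputs** (values in multiples of ULN, except INR):
- Entry: liver test < 1.5 (inclusion 5).
- 7.4.1: (TBL > 2 or INR > 1.5) AND (AST > 3 with baseline AST < 1, or ALT > 3 with baseline ALT < 1) AND no other apparent cause.
- 7.4.2: max(AST, ALT) > 8; or between 5 and 8 for at least 2 weeks or unmonitored; or symptoms; or TBL > 3; or ALP > 8.

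**Assumptions:** no other cause apparent, ALP normal, monitoring adhered to, and no symptoms unless stated. INR is at most 1.5 unless stated.

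| Baseline AST / ALT | On-study AST and ALT | TBL, other | 7.4.1 | 7.4.2 |
|---|---|---|---|---|
| 0.9 / 0.9 | 4 | 2.5 | permanent stop | not needed |
| 1.2 / 0.9 | 4 | 2.5 | permanent stop, through ALT | not needed |
| 1.2 / 1.2 | 4 | 2.5 | no | no |
| 1.2 / 1.2 | 4 | 1.5, INR 1.7 | no | no |
| 1.2 / 1.2 | 6, under 2 weeks | 2.5 | no | no |
| 1.2 / 1.2 | 6, at least 2 weeks | 2.5 | no | hold |
| 1.2 / 1.2 | 4 | 3.1 | no | hold |
| 1.2 / 1.2 | 4 | 2.5, hepatitis symptoms | no | hold |

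The second row shows why both enzymes must be raised: one enzyme below ULN at baseline can still trigger the stop. A baseline exactly at ULN also falls in the gap, because the condition is strictly below ULN.

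**The uncovered band.** With both enzymes at or above ULN at baseline and no symptoms, no hold is mandatory for AST/ALT > 3 to 5 × ULN combined with TBL > 2 to 3 × ULN, or combined with INR > 1.5 while TBL is at most 3 × ULN. The band extends up to 8 × ULN while the elevation has lasted under 2 weeks and the subject is monitored.

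**How far the trigger moves:**
- At TBL 2.5 × ULN, the transaminase level that forces a hold moves from > 3 × ULN to > 8 × ULN (or > 5 × ULN if sustained or unmonitored).
- From a baseline near 1.5 × ULN, the required rise is 8 / 1.5 = 5.3-fold (or 5 / 1.5 = 3.3-fold) instead of 3 / 1.5 = 2-fold.
- At AST/ALT 4 × ULN, the bilirubin level that forces a hold moves from > 2 to > 3 × ULN.
- At AST/ALT 4 × ULN with TBL at most 3 × ULN and no symptoms, no INR value forces a hold.

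**Reporting and analysis for the uncovered rows.** The bilirubin case (TBL 2.5) fits the Appendix 3 parenthesis but not the Section 7.4 criteria to which that sentence refers, so the 24-hour report is ambiguous. In SAP 9.2 this subject counts under TBL but not under AST/ALT. The INR case (TBL 1.5, INR 1.7) lies outside the Appendix 3 parenthesis and meets neither named SAP criterion.

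**With the baseline condition removed,** every uncovered row becomes a permanent stop. Results for subjects with baseline below ULN do not change.

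**The case against.** The strongest reply is that the gap is small and well guarded. It needs both enzymes raised but below 1.5 × ULN at entry and judged unimportant, with hepatitis B and C and a positive alcohol test already excluded. It then needs a combined on-study signal with none of a broad list of hepatitis signs, in a trial of about 20 subjects. Several controls have no baseline condition:

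- Appendix 3 puts anyone with AST/ALT > 3 × ULN under close observation, with retesting within 24 hours when TBL exceeds 2 × ULN, at least twice-weekly monitoring at first, and specialist consultation.
- Protocol 10.1.1 captures as an adverse event "Any clinically important test abnormality that suggests a disease and/or organ toxicity that has worsened or is new" and "Any test abnormality that required the subject to receive specific corrective therapy, close observation, more frequent follow-up assessment".
- The IDMC reviews data regularly, and the investigator or sponsor may withdraw a subject for an adverse event.
- Ordinary SAE criteria apply, and SAP 9.2.2 lists all chemistry with out-of-range values flagged.

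All of this stands and limits the weight of the point. These controls observe, record or permit, however. None directs that the drug be stopped. The closing paragraph of 7.4.1 requires a decision but sets no default.

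Two narrower replies have partial force. The lost rechallenge bar matters only if the drug is stopped by discretion, and unanimous agreement is then still needed. INR is not in the Appendix 2 panel and is obtained in the Appendix 3 work-up, so the subject is already under observation when it is known. Even so, a result above 1.5 at that point triggers no hold.

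The baseline condition could also be deliberate, since 7.4.2 expressly disregards baseline and 7.4.1 does not. The guidance cited in 7.4 is not available here, so intent cannot be settled. But no rationale is given, and the Appendix 3 statement about normal liver function suggests a mismatch with inclusion 5.

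**Conclusion.** The concern holds. A stated safety rule is weaker for a group of subjects that the trial admits. In the band described, identical on-study values force a permanent stop from a normal baseline and no hold from a raised one. This rests on a literal reading of 7.4.1, no other apparent cause, no symptoms, and both enzymes at or above ULN at baseline.

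The zone is narrow, and its frequency cannot be derived from the documents. No efficacy analysis is affected. The SAP consequence is modest, because the bilirubin case still appears under the TBL criterion and in the flagged listing. It should be corrected as a matter of sound safety drafting, but it does not threaten the trial's conclusions.

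**What to change.** 1. **Protocol 7.4.1:** delete the baseline condition, so that AST or ALT > 3 × ULN applies to every subject. Keep the TBL/INR and no-other-cause limbs. Since eligible Screening values are below 1.5 × ULN, exceeding 3 × ULN is still more than a 2-fold rise over any of them.
2. **Appendix 3:** replace the statement about normal liver function with the inclusion 5 limit, and name TBL > 2 × ULN or INR > 1.5, so that the 24-hour report plainly covers all subjects.
3. **SAP 9.2:** count concurrent AST/ALT > 3 × ULN with TBL > 2 × ULN (or INR > 1.5 where obtained) at any baseline, flagged by baseline status (< ULN, ≥ ULN), in the existing DILI table.

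A baseline-relative threshold or a temporary hold for raised-baseline subjects would also close the gap. Deleting the condition is simplest and treats all subjects alike.

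The cost is two wording changes in a protocol amendment with ethics committee approval (Protocol 13.4) and one SAP criterion. The downside is possibly an occasional extra permanent stop in a subject whose enzymes were raised at baseline.
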